	
Endpoint: Incidence of PCR-adjusted parasitemia (thick smear/microscopy, after adjustment for parasitemia due to new infections as determined by genotyping using PCR techniques).
 
Population: See primary endpoint
 
Treatment: See primary endpoint
	3

Objectives	Estimands/Endpoints	Ref. #
	
Intercurrent Event Strategy: See endpoint #2
 
Population-Level Summary: See endpoint #2
 
Endpoint: Incidence of PCR-adjusted parasitemia (thick smear/microscopy, after adjustment for parasitemia due to recrudescence as determined by genotyping using PCR techniques).
 
Population: see primary endpoint
 
Treatment: See primary endpoint
 
Intercurrent Event Strategy: See endpoint #2
 
Population-Level Summary: See endpoint #2
	4
To evaluate the parasite clearance time in adults and adolescents with asymptomatic P. falciparum malaria treated with different doses of M5717 in combination with pyronaridine	
Endpoint: Parasite clearance time defined as time from dosing to the first negative (no parasites) blood film (microscopy)
 
Target Population: See primary endpoint
 
Treatment: See primary endpoint
 
Intercurrent Event Strategy:
 
 • Intake of rescue medication after study treatment and before negative blood smear: treatment policy strategy, i.e. treatment effect is estimated regardless of ICE • Intake of antibiotics or other prohibited medication that impacts treatment effect (e.g. drug with antimalarial activity) at the time or after the time of study treatment, but before first negative blood smear: Treatment policy strategy • Experience of any event that affects absorption (i.e. vomiting within the first 24 hours after dosing): Treatment policy strategy, i.e. treatment effect is estimated regardless of ICE • Death before negative blood smear: On-treatment strategy, i.e. time to parasite clearance is censored at the time of death 
Population-level Summary: Median parasite clearance time as estimated by Kaplan-Meier method for each dose of M5717
	5
To evaluate the safety and tolerability of different doses of M5717 in combination with pyronaridine in adults and adolescents with asymptomatic P. falciparum malaria	Endpoint: Incidence, severity, and seriousness of TEAEs, treatment-emergent study intervention related AEs, as per CTCAE v 5.0	6

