To characterize the PK profile of the M5717plus pyronaridine combination	PK parameters of M5717 and pyronaridine using noncompartmental analysis, as appropriate.	7

Objectives	Estimands/Endpoints	Ref. #
CCI		

6 Overview of Planned Analyses

This IAP covers analyses of efficacy, pharmacokinetic (PK), pharmacodynamic (PD), and safety based on the data at the end of the study.

7 Changes to the Planned Analyses in the Clinical Study Protocol

- For estimand #5 (time to parasite clearance) the intercurrent event strategies were changed. Applying ICE handling strategies equivalent to estimand #2, as defined in the protocol, was not adequate.

- CCI

8 Analysis Sets and Subgroups

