- **Death due to malaria or other reasons:** filter SAEs programmatically for fatal events with outcome "death" and by medical/safety review. Death cases for which the primary reason is ticked as "progressive disease and/or disease-related condition" qualify as death due to malaria. A composite variable strategy is applied if the death was due to malaria (i.e. a parasitemia event is considered at the time of death) and an on-treatment strategy is defined if death was due to other reasons (i.e. time to parasitemia is censored at the time of death)

The population-level summary is defined as the Hazard Ratios (HRs) for each dose of M5717 relative to the untreated participants in Cohort 4. HRs are estimated from a Cox Proportional Hazards Model with time to parasitemia included as the dependent variable and dose cohorts, site and sex included as independent factors, and baseline age, body weight and parasite density included as independent covariates. Participants will be censored in case of occurrence of an ICE as described above, at the last available visit in case of premature study discontinuation or at the end of study in case no parasitemia event was observed.

For the multivariable (primary) model, a table showing HRs together with 95% Wald CIs will be provided which will contain in addition estimates of coefficients, SEs and p-values (based on Likelihood Ratio Test) in order to assess whether the factors and covariates included into the model have a significant influence on the time to parasitemia. As additional information a table providing information on censoring frequency and occurrence of ICEs will be provided.

As part of descriptive analyses of the primary endpoint, which also covers the analysis of the second estimand (incidence of parasitemia), a table displaying number and percentages of

parasitemia events (estimated directly from the data) will be provided together with estimates of a Kaplan-Meier (KM) analysis. Median time of protection and 95% CI will be estimated using the KM method for each cohort. As a graphical illustration, a KM-figure will be provided showing time to parasitemia in days after parasite clearance.

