14.2.3 Parasite Clearance Time

For estimating parasite clearance time (in hours), which is the time from dosing (first dose in the Malarone treatment cohort) to the first negative blood film (parasite count of 0 on microscopy), followed at least by 1 subsequent visit with a negative blood film. Patients should not be considered for analysis if they did not have parasites >0 at any timepoint. The same ICEs as defined in Section 5 will be considered. The median parasite clearance time will be estimated by use of Kaplan-Meier method for each cohort. Participants will be censored in case of occurrence of an ICE if the ICE occurred before the first negative blood film, at the last available visit in case of premature study discontinuation before the first negative blood film or at the end of study in case no parasite clearance event was observed.

15 Safety Analyses

This section includes specifications for summarizing safety endpoints that are common across clinical studies such as adverse events, laboratory tests and vital signs.

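### SAP 14.2.3 censors parasite clearance time at any intercurrent event, whereas SAP Section 5 censors it only at death

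*SAP*

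**What the plan says.** SAP Section 5 (endpoint 5) gives one strategy for each of four intercurrent events that may precede clearance:

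- Rescue medication: "Intake of rescue medication after study treatment and before negative blood smear: treatment policy strategy, i.e. treatment effect is estimated regardless of ICE".
- Antibiotics or other prohibited medication, from dosing onward: "but before first negative blood smear: Treatment policy strategy".
- Absorption events: "Experience of any event that affects absorption (i.e. vomiting within the first 24 hours after dosing): Treatment policy strategy".
- Death: "Death before negative blood smear: On-treatment strategy, i.e. time to parasite clearance is censored at the time of death".

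Section 7 explains that these differ from the protocol on purpose: "Applying ICE handling strategies equivalent to estimand #2, as defined in the protocol, was not adequate".

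Section 14.2.3, which specifies the analysis, says "The same ICEs as defined in Section 5 will be considered" and then gives the censoring rule: "Participants will be censored in case of occurrence of an ICE if the ICE occurred before the first negative blood film". The same sentence also censors at the last visit for early discontinuation and at end of study if clearance was never seen. The summary is the Kaplan-Meier median for each cohort.

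**The concern.** The two sections give different instructions for the same endpoint. Under treatment policy, a participant who vomits, takes rescue medication or takes an antibiotic before clearing still contributes the clearance time that was observed. Under 14.2.3 as written, that participant leaves the risk set at the event. The Kaplan-Meier method then treats them as if they would have cleared like those who remain. That assumption is doubtful for an event whose defining feature is impaired absorption.

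Vomiting is the most likely trigger. Its window is the first 24 hours, which overlaps the early blood films at 1, 6, 12 and 24 h in Cohorts 1 to 3 (protocol Table 2). If such events slow clearance, censoring makes the clearance curve look faster than the declared estimand would show, and by different amounts if the events are unevenly spread across cohorts.

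Two programmers could each follow the SAP faithfully and report different results. The study is open label, so settling the question after the data have been seen would leave the choice open to challenge.

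**Working it through.** **Step 1: compare the two sections event by event.** The plan states no figure for this point, so there is none to reproduce.

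| Event before first negative film | Section 5, endpoint 5 | 14.2.3 as written | Agree? |
|---|---|---|---|
| Rescue medication | treatment policy | censor | no |
| Antibiotics / prohibited medication | treatment policy | censor | no |
| Event affecting absorption | treatment policy | censor | no |
| Death | censor | censor | yes |

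Three of four conflict.

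**Step 2: does the reference to Section 5 carry the strategies across?** Section 14.2.3 imports the events and then adds its own unqualified rule. Section 14.2.2 (PCR-adjusted parasitemia), by contrast, says that both the events and their strategies are taken over from the primary estimand. The condition that the event must come before the first negative film also adds little if death is the only event meant. It has a clear purpose for vomiting, rescue or antibiotics.

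**Step 3: illustrate the consequence.** From the documents: 45 per cohort (protocol 9.2), and films at 1, 6, 12 and 24 h (Table 2), then Day 3 and Day 4 (about 48 and 72 h) and weekly from Day 8 (Table 1). Assumptions, none of them in the documents:

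- Clearance time is Weibull with shape 2 and true median 30 h, so the uncleared proportion is S(t) = 2^(−(t/30)²).
- A proportion p = 5%, 10% or 20% vomits within 0 to 6 h of dosing.
- Vomiting either leaves clearance time unchanged or doubles it.
- The first negative film is taken as clearance. The SAP's confirmatory second negative film is not modelled.

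Observed clearances per cohort under 14.2.3 are about 45 × (1 − p):

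- p = 5%: 45 × 0.95 = 42.75 (simulated 42.7)
- p = 10%: 45 × 0.90 = 40.5 (simulated 40.5)
- p = 20%: 45 × 0.80 = 36.0 (simulated 36.0)

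Under treatment policy all 45 contribute.

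Uncleared at 48 h:

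- Non-vomiters: S(48) = 2^(−2.56) = 0.170.
- Vomiters with doubled time: S(24) = 2^(−0.64) = 0.642.
- Treatment policy mixes the two, (1 − p) × 0.170 + p × 0.642, which gives 0.19, 0.22 and 0.26 for the three rates.
- Censoring stays at about 0.17 throughout.

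A simulation with 200,000 draws gave 0.194, 0.218 and 0.264 under treatment policy, against 0.170 to 0.171 under censoring. When vomiting did not change clearance time, the two curves coincided.

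**Step 4: the median, which is the reported summary.** At 24 h the simulated uncleared proportion was 0.655, 0.668 and 0.693 under treatment policy and 0.642 to 0.643 under censoring. All of these exceed 0.5, and all the 48 h values are below it, so the film-schedule median was 48 h under both rules in every scenario. It would move only if, at some film, the two curves fell on opposite sides of 0.5.

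**The case against.** The best defence is that the intended rule can be recovered. Section 14.2.3 points to Section 5, Section 7 says the strategies were changed deliberately, and the modification history says version 2.0 resolved inconsistencies in intercurrent events for some estimands. On that view the censoring sentence is a leftover, and a careful programmer would censor only at death. This is a plausible account of how the text arose, but it is an inference. The sentence still states the opposite for three events, and nothing in 14.2.3 limits it.

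A second defence is that little hangs on it. The endpoint is secondary, the protocol (9.1) describes all analyses as descriptive, and the illustrated median did not move. That stands, and it limits the severity.

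A reader might also infer that the primary analysis has the same fault, because 14.1.1 says "Participants will be censored in case of occurrence of an ICE as described above", and that rescue and malaria deaths there would turn from events into censored observations. The documents do not support this. The closing words of that quote refer to a list just before it that fixes the handling of each event: rescue and malaria death count as failures, antibiotics or prohibited medication and other deaths are censored, and absorption events follow treatment policy. Section 14.1.2 confirms it, since its sensitivity analysis replaces treatment policy with censoring for absorption events. That would be pointless if the main analysis already censored them.

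**Conclusion.** The contradiction is real and lies within the current SAP: three of four intercurrent events for clearance time are handled in opposite ways, and only death agrees. As written, 14.2.3 does not estimate the estimand declared in Section 5. This part rests on the text alone.

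The numerical effect depends on assumptions. The documents give neither a vomiting rate nor a relation between vomiting and clearance. If 5% to 20% vomit early and take twice as long to clear, the uncleared proportion at 48 h differs by about 0.02 to 0.09 between the rules (0.194 − 0.170 = 0.024; 0.264 − 0.170 = 0.094). If vomiting does not slow clearance, there is no bias, only fewer observed clearances. The corresponding loss, up to about 2 to 9 of 45 per cohort, is an upper bound at those rates, because vomiting after the first negative film has no effect. Rescue and antibiotic use were not modelled, and the direction of their effect is not settled by the documents.

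A reader might conclude that censoring shortens the median clearance time. That has not been shown: the effect on the median may be small or nil.

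This should be fixed. It is not critical, because the endpoint is secondary and descriptive and the primary analysis is unaffected.

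**What to change.** Replace the censoring sentence in SAP 14.2.3 with wording such as:

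*Clearance time is censored only at death before the first negative film, at the final attended visit for participants who leave the study before clearing, and at end of study for those in whom clearance was never observed. Rescue medication, antibiotics or other prohibited medication, and events affecting absorption do not lead to censoring; they are handled by treatment policy as set out in Section 5.*

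If wider censoring is what the sponsor wants, keep 14.2.3 and change Sections 5 and 7 to match, with a reason. Either way, settle it before database lock.

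The cost is one SAP sentence. Section 14.1.1 needs no change and no further analysis is required.

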15.1 Adverse Events

Adverse Events will be coded according to MedDRA version 27.1. The severity of AEs will be graded using CTCAE v5.0.

Treatment-emergent AEs (TEAEs) are those events with onset or worsening dates on or after the first administration of study intervention. In case an AE starts on the day of study treatment administration and the AE start time is partially or completely missing, the AE is considered as treatment-emergent.

Any AE occurring before the administration of study intervention on Day 1 and resolved before administration of study intervention or not worsening after administration of study intervention will be included in the AE listings but will not be included in the summary tables (unless otherwise stated). These will be referred to as “pre-treatment” AEs.

Related AEs are those AEs with relationship to study treatment reported by the investigator as related or those of unknown relationship.

Serious AEs are those events reported on the AE eCRF form with the serious field ticked “Yes” or with unknown seriousness.

AEs leading to study discontinuation are those AEs that were referenced as reason for early study termination on the eCRF study termination page.

AEs of special interest are liver (AT increase, TB increase) and CNS signals which will be specifically followed-up through laboratory surveillance and a specific physical examination at specific visits during the study. AESIs are AEs which have been ticked to qualify as events of special interest per protocol on the AE eCRF form. In addition, a list of PTs will be appended to the table shells document with which AEs qualifying as AESIs will be identified.

Group/SOC terms will be sorted alphabetically. Preferred terms within each group/SOC will be sorted by descending frequency in the highest dose cohort, and alphabetically if multiple preferred terms have the same frequency.

If a participant experiences more than one occurrence of the same TEAE during the trial, the participant will only be counted once for that treatment (the worst severity and the worst relationship to trial treatment will be tabulated).

In case a participant had events with missing and non-missing grades, the maximum of the non-missing grades will be displayed. AEs with missing classification concerning study intervention relationship will be considered related to the study intervention.

Incomplete AE-related dates will be handled as described in Section 9.13.

15.1.1 Overview of TEAEs

An overall summary of TEAEs will be provided including frequencies of participants experiencing at least any

- TEAE
- TEAE leading to study termination
- Related TEAE
- Serious TEAE
- Related serious TEAE
- TEAE by intensity (NCI-CTCAE grades 1-4)
- Related TEAE by intensity (NCI-CTCAE grades 1-4)
- AESI
- Related AESI
- TEAE leading to death
- Related TEAE leading to death

Frequency tables of TEAEs by SOC and PT will be provided for:

- All TEAEs
- TEAEs at a frequency threshold of 5%
- Serious TEAEs
- TEAEs leading to study termination
- TEAEs leading to death
- Related TEAEs
- Related serious TEAEs
- Related TEAEs leading to study termination
- Related TEAEs leading to death
- TEAEs of special interest

More specifically, tables displaying TEAEs by worst grade, SOC and PTs will be provided, separated by treatment cohorts. A graphical presentation of TEAEs occurring in $>10\%$ of participants will be provided separately for each treatment cohort as well.

15.1.2 The 3-Tier Approach

The 3-tier approach for summarizing and analyzing AEs in clinical studies will be followed. AEs in different tiers are analyzed using different types of statistical analysis.

The AEs identified for Tier 1 reporting are listed in below table together with the description how Tier 1 AEs will be analyzed:

Tier 1 AE	Within group summary	Between group comparison (Each dose cohort – natural infection cohort) 95% CI
Nervous system disorders (SOC 10029205)	n (%)	Δ [xx%, xx%]
ALT increased (PT 10001551)		
ALT abnormal (PT 10001547)		
AST increased (PT 10003481)		
AST abnormal (PT 10003477)		
AST/ALT ratio abnormal (PT 10082832)*		

* either documented AE or AST/ALT=abnormal in laboratory data. An AST/ALT ratio between 0.7 and 1.4 is thereby interpreted as “normal”. Values outside of this range are “abnormal”.

All Tier 1 events will be summarized in a table. Incidence rates and differences in incidence rates between each dose cohort and the natural infection cohort will be provided together with 95% CIs for the differences in incidence rates. For Tier 1 events which were observed for less than 3 participants the CIs will not be displayed in the Tier 1 table. 95% CIs for the differences in incidence rates will be estimated using Miettinen & Nurminen method. For graphical illustration a forest plot will be provided separately for the different treatment cohorts.

All TEAEs for which any PT or SOC is observed in 4 or more participants in any cohort are defined to be Tier 2 AEs. Tier 2 AEs are thus used for signal detection among common events. A frequency table by SOC and PT will be provided together with differences in incidence and 95% CI comparing different dose groups to the natural infection cohort. While analyses will be done for all Tier 2 TEAEs, only TEAEs with incidence proportion $\geq 5\%$ in at least one cohort will be presented in the body of CSR. No multiplicity adjustment will be applied.

Remaining TEAEs are defined as TIER 3 AEs and frequencies of participants with at least one Tier 3 TEAE will be provided by SOC and PT.

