Visit Number	Prescreening	Scr + Visit 1 ^a	Visit 2 ^a	Visit 3	Visit 4	Visits 5 to 12	Visit 13	Unscheduled Visit	
^a Visit 1 and 2: Participants randomized to Cohorts 1 to 3 will remain in hospital or stay in the vicinity of the sites for 24 hours for PK sampling and assessment of parasitemia (see Table 2).
 
Participants randomized to Cohort 4, will visit the clinic on Days 1, 2, and 3 for dosing in an outpatient setting
	
Timepoint	Prescreening	Day 1	Day 2	Day 3	Day 4	Week 2 to 9 (weekly visits starting at Day 8)	EOS (last visit) Week 10, Day 64 ^b	Can be required due to AEs, and AESIs; follow-up of AEs and AESIs	
^b Day 64 or day of completion or premature discontinuation.
 
Participants will remain in the study until parasitemia or until Day 64, whichever comes first.
 
All EOS evaluations will be completed before providing antimalarial rescue treatment if required.
	
Blood films (microscopy)		X	X	X	X	X	X		
Thick and thin blood films will be collected at Visit 1 (predose) to confirm eligibility and at all visits.
 
Cohorts 1 to 3: The exact timepoints on Days 1 to 2 are provided in Table 2.
 
Cohort 4: Blood films should be examined at Screening, predose on Day 1, Day 2, and Day 3.
 
Blood sampling for parasitemia will be done simultaneously with PK.
	
Inclusion/ exclusion criteria		X								
COVID-19 antigen test		X							
The test will be conducted at Visit 1. Additional COVID-19 tests may be conducted as needed.
	
Demographic and medical history		X								
Randomization		X								

Assessments & Procedures	Outpatient	Outpatient/Inpatient ^a		Outpatient					Notes	
Visit Number	Prescreening	Scr + Visit 1 ^a	Visit 2 ^a	Visit 3	Visit 4	Visits 5 to 12	Visit 13	Unscheduled Visit	
^a Visit 1 and 2: Participants randomized to Cohorts 1 to 3 will remain in hospital or stay in the vicinity of the sites for 24 hours for PK sampling and assessment of parasitemia (see Table 2).
 
Participants randomized to Cohort 4, will visit the clinic on Days 1, 2, and 3 for dosing in an outpatient setting
	

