8.3.6 Adverse Events of Special Interest

Liver events (AT increase, TB increase) and CNS events will be considered AESIs and specifically followed-up through laboratory surveillance and a specific physical examination at specific visits during the follow-up. All those events should be reported to the Sponsor within 24 hours of knowledge and appropriate updates should be provided when new information becomes available.

For this study, AESI(s) include only the following:

- Liver events will be monitored through LFTs that will include the 2 ATs, ALT, and AST, as well as TB and ALP. Specific details regarding the values confirmation, follow-up, and monitoring frequency are provided in [Appendix 6](#).
- Neurological events will be monitored through specific neurological clinical examinations, detailed in [Section 8.2.1](#). This neurological physical examination will be done at Screening and at every visit. If additional tests or assessments (such as CT, MRI, lumbar puncture) are required to further evaluate neurological abnormalities detected, those will be done at the discretion of the Investigator.

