15.2.5 Clinical Laboratory Evaluation

The following laboratory parameters will be measured during the trial and reported as part of the safety evaluation (for a detailed list of parameters refer to Appendix 10 of the CTP):

- Hematology
- Biochemistry

Summary tables over time displaying absolute values and changes from Baseline will be provided. For a graphical presentation line plots of lab parameters standardized to times ULN over time will be provided for each participant. Thereby, plots should be grouped by participants of different cohorts and by lab parameters in the following way:

- Biochemistry:

- Alanine Aminotransferase, Alkaline Phosphatase, Aspartate Aminotransferase, Bilirubin
- Calcium, Creatinine, Glucose, Chloride
- Potassium, Protein, Sodium
- Hematology:
 - Basophils, Eosinophils
 - Hematocrit, Hemoglobin
 - Leukocytes, Lymphocytes, Monocytes, Neutrophils, Platelets, Reticulocytes

In addition, shift tables from Baseline based on normal ranges will be given.

In order to investigate possible events of Hy's Law, an eDISH Plot will be provided

Outputs will be presented using the Merck Standard Unit Catalogue (see Appendix 2). Normal ranges will be provided by the local laboratories, and out of range flags will be calculated based on the normal ranges. Laboratory data not transferred in standard units will be converted to before processing. Both original units and standard units will be provided in the SDTM domain.

Subject Data Listings will only be provided for subjects with abnormal test results (lower than LLN and higher than ULN, abnormal CS and abnormal NCS).

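### One Tier 1 liver row counts any laboratory AST/ALT ratio outside 0.7 to 1.4 whatever the enzyme levels, and Tier 1 has no bilirubin row

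*SAP*

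**What the plan says.** SAP 15.1.2 names the nervous system disorders class and five liver terms as Tier 1: ALT increased, ALT abnormal, AST increased, AST abnormal and AST/ALT ratio abnormal. Each row gets incidences per cohort and a difference from the natural infection cohort with a Miettinen-Nurminen 95% interval, except that intervals are not shown for events seen in fewer than 3 participants.

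Four of the liver rows, such as "ALT increased (PT 10001551") and "AST increased (PT 10003481"), are identified by preferred term only. The fifth, "AST/ALT ratio abnormal (PT 10082832"), carries a footnote that adds a laboratory criterion: "either documented AE or AST/ALT=abnormal in laboratory data. An AST/ALT ratio between 0.7 and 1.4 is thereby interpreted as" normal, with anything outside that range abnormal.

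Protocol 8.3.6 states: "Liver events (AT increase, TB increase) and CNS events will be considered AESIs". SAP 15.1 repeats it: "AEs of special interest are liver (AT increase, TB increase) and CNS signals". No Tier 1 row concerns bilirubin. In SAP 15.1.2 a term enters Tier 2, where between-cohort intervals are also given, if it is seen in 4 or more participants in any cohort. Everything else is Tier 3 and gets frequencies only.

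Elsewhere, SAP 15.2.5 plans laboratory summaries, plots in multiples of ULN, shift tables and, for possible Hy's Law cases, "an eDISH Plot will be provided".

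**The concern.** Every liver criterion in the protocol is an absolute level or grade: ALT above 3 x ULN and/or total bilirubin above 2 x ULN (Table 1), Hy's law and Grade 3 or higher transaminase increases (Section 4.1), and the DILI definition (Appendix 6). None uses an AST/ALT ratio.

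A ratio carries no information on level. The footnote's criterion can therefore report normal enzymes as a liver event and cannot register a proportional rise of both enzymes. As written it does not even exclude the predose sample. The SAP's treatment-emergent definition is framed for adverse events, not for a laboratory criterion.

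This matters because it is the only Tier 1 row that looks at measured values. The ALT and AST rows depend on the investigator judging a change clinically significant enough to record as an adverse event (Protocol 8.2.4 and Appendix 5), in an open-label study. At stake is whether the planned between-cohort comparison for a named event of special interest measures liver injury or background variation.

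**Working it through.** **1. The rule applied to examples.** The documents give no ULN in units, so 40 U/L is assumed for both enzymes.

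| AST | ALT | Enzymes | AST/ALT | Ratio row |
|---|---|---|---|---|
| 24 | 15 | both normal | 1.60 | event |
| 30 | 20 | both normal | 1.50 | event |
| 14 | 22 | both normal | 0.64 | event |
| 400 | 400 | both 10 x ULN | 1.00 | no event |
| 400 | 300 | 10 x and 7.5 x ULN | 1.33 | no event |
| 400 | 250 | 10 x and 6.25 x ULN | 1.60 | event |

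Multiplying both values by the same factor leaves the ratio unchanged, so a proportional rise from a ratio inside the range never triggers the row. A cut-off of ALT or AST above 3 x ULN (120 U/L here) reverses the first five classifications. The SAP does not say whether the ratio uses raw values or multiples of ULN.

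**2. How often a participant with no liver effect is flagged.** Table 1 schedules chemistry after Day 1 on Days 2, 3 and 4 (3 draws), at Visits 5 to 12 (8) and at Visit 13 (1), so 12 draws. Entry excludes AST or ALT above 1.5 x ULN (Protocol 5.2), so most participants start normal or near normal. The per-draw rate p of an out-of-range ratio is not in the documents. With independent draws, P(ever flagged) = 1 - (1 - p)^12:

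- p = 2%: 21%
- p = 5%: 46%
- p = 10%: 72%
- p = 20%: 93%

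Repeated draws in one person are correlated. Simulating a log-normal ratio (median 0.9 to 1.3, SD of the log 0.15 to 0.35, within-person correlation 0.5 to 0.8, all assumed) gives 9% to 97%.

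**3. Effect on this row's comparison.** With 45 per cohort (Protocol 9.2), take an excess of 5 participants, 5/45 = 11.1 points. The Miettinen-Nurminen 95% interval is +2.8 to +23.6 points for 5/45 against 0/45, but -9.5 to +30.7 for 23/45 against 18/45. If true events of 15% against 2% (assumed) are all counted inside this row, power is 60% with no background flags, 20% with 20% background and 11% with 40%.

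**4. Bias from unequal follow-up.** Protocol Table 1, note b: "Participants will remain in the study until parasitemia or until Day 64, whichever comes first". Take 63% and 87% free of parasitemia (Protocol 9.2) as reached over 63 days at constant hazard, with no dropout and exit at the detecting weekly visit. With S the final proportion, the expected post-dose draws are 3 plus the sum of S^(j/9) for j = 0 to 8, that is 3 + (1 - S)/(1 - S^(1/9)):

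- Cohort 4: 3 + 0.37/0.0500 = 10.4
- Highest dose: 3 + 0.13/0.01535 = 11.5

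Averaging 1 - (1 - p)^k over the exit distribution, k being the number of draws, gives these ever-flagged proportions:

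| p | Cohort 4 | Highest dose | Spurious excess |
|---|---|---|---|
| 2% | 18.8% | 20.6% | 1.8 points |
| 5% | 40.8% | 44.2% | 3.5 points |
| 10% | 65.1% | 69.6% | 4.5 points |
| 20% | 87.9% | 91.4% | 3.6 points |

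The excess is about 2-4 points, or 1 to 2 participants of 45.

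**5. Bilirubin.** A bilirubin term seen in 3 participants in each of the three dose cohorts (9 of 135) does not reach 4 in any cohort. As a term it falls to Tier 3, with no between-cohort interval of its own.

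**The case against.** The strongest reply is that the footnote governs one row of five. A 10-fold rise of both enzymes should be recorded as an adverse event: clinically significant laboratory changes are recorded, aminotransferase increase is an event of special interest reportable within 24 hours, and values above 3 x ULN prompt repeat testing. It would then appear in the ALT and AST rows, which are estimated separately and which false flags in the ratio row cannot dilute. Shift tables, plots in multiples of ULN and the eDISH plot would show it too. Bilirubin is in the special-interest table and those laboratory outputs, and reaches Tier 2 if common enough. The study is descriptive with no confirmatory testing (Protocol 9.1), and its safety stopping criteria do not use Tier 1.

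All of that stands, and it rules out several stronger readings that a reader might infer:

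- That the plan as a whole calls a 10-fold rise normal. Only this row does.
- That noise hides a signal across Tier 1. The power loss in step 3 applies only to events counted inside the ratio row.
- That bilirubin is missing from the safety analysis. It is missing from Tier 1 only.
- That most of each cohort will be flagged. The assumed range of 9-97% cannot establish this.
- That follow-up bias is large. Setting 5 draws (exit at Day 15) against 12 gives 23% against 46% at p = 5%, but this compares individuals. Only about 10% of Cohort 4 would leave by Day 15 under the protocol's assumption.

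What the reply does not answer is that the row yields wrong event counts by its own definition, and that the other outputs do not supply between-cohort differences for measured liver values.

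**Conclusion.** The point holds for one Tier 1 row and for the absence of bilirubin from Tier 1. That the ratio row can count normal enzymes and cannot register a proportional rise follows from the rule itself and needs no assumption. Its risk differences and intervals would mix background ratio variation with liver events. The size of that mixing is not in the documents and rests wholly on the assumed per-draw rate and correlation. The follow-up bias runs against the dose cohorts but is small, and noise is the main harm. The primary endpoint and the other liver outputs are unaffected. The row should still be changed, because it is a prespecified safety comparison for a named event of special interest and is wrong as written.

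**What to change.** In SAP 15.1.2:

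1. Delete the laboratory criterion from the AST/ALT ratio row, leaving documented adverse events only.
2. Add Tier 1 rows for post-baseline laboratory ALT or AST above 3 x ULN, total bilirubin above 2 x ULN, and both together. These are the levels already stated in Protocol Table 1 and Appendix 6.
3. Add the bilirubin-increased preferred term to the Tier 1 list.

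The cost is a change to one SAP table and its shells. ALT, AST and total bilirubin are already collected (Protocol Appendix 10) and already expressed in multiples of ULN for SAP 15.2.5. No new assessment and no change to participant management is involved. The new rows would keep a slight dependence on length of follow-up, which a note beside the table can state.
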